### 5.7.5 Supportive Care Guidelines for Pembrolizumab

Subjects should receive appropriate supportive care measures as deemed necessary by the treating investigator. Suggested supportive care measures for the management of adverse events with potential immunologic etiology are outlined below. Where appropriate, these guidelines include the use of oral or intravenous treatment with corticosteroids as well as additional anti-inflammatory agents if symptoms do not improve with administration of corticosteroids. Note that several courses of steroid tapering may be necessary as symptoms may worsen when the steroid dose is decreased. For each disorder, attempts should be made to rule out other causes such as metastatic disease or bacterial or viral infection, which might require additional supportive care. The treatment guidelines are intended to be applied when the investigator determines the events to be related to pembrolizumab.

Note: if after the evaluation the event is determined not to be related, the investigator does not need to follow the treatment guidance (as outlined below). Refer to Section 5.2.1 for dose modification.

It may be necessary to perform conditional procedures such as bronchoscopy, endoscopy, or skin photography as part of evaluation of the event.

- **Pneumonitis:**
  - For **Grade 2 events**, treat with systemic corticosteroids. When symptoms improve to Grade 1 or less, steroid taper should be started and continued over no less than 4 weeks.
  - For **Grade 3-4 events**, immediately treat with intravenous steroids.  
Administer additional anti-inflammatory measures, as needed.

- Add prophylactic antibiotics for opportunistic infections in the case of prolonged steroid administration.
- **Diarrhea/Colitis:**  
Subjects should be carefully monitored for signs and symptoms of enterocolitis (such as diarrhea, abdominal pain, blood or mucus in stool, with or without fever) and of bowel perforation (such as peritoneal signs and ileus).
  - All subjects who experience diarrhea/colitis should be advised to drink liberal quantities of clear fluids. If sufficient oral fluid intake is not feasible, fluid and electrolytes should be substituted via IV infusion. For Grade 2 or higher diarrhea, consider GI consultation and endoscopy to confirm or rule out colitis.
  - For **Grade 2 diarrhea/colitis**, administer oral corticosteroids.
  - For **Grade 3 or 4 diarrhea/colitis**, treat with intravenous steroids followed by high dose oral steroids.
  - When symptoms improve to Grade 1 or less, steroid taper should be started and continued over no less than 4 weeks.
- **Type 1 diabetes mellitus (if new onset, including diabetic ketoacidosis [DKA]) or  $\geq$  Grade 3 Hyperglycemia, if associated with ketosis (ketonuria) or metabolic acidosis (DKA)**
  - For **T1DM** or **Grade 3-4** Hyperglycemia
    - Insulin replacement therapy is recommended for Type I diabetes mellitus and for Grade 3-4 hyperglycemia associated with metabolic acidosis or ketonuria.
    - Evaluate patients with serum glucose and a metabolic panel, urine ketones, glycosylated hemoglobin, and C-peptide.
- **Hypophysitis:**
  - For **Grade 2** events, treat with corticosteroids. When symptoms improve to Grade 1 or less, steroid taper should be started and continued over no less than 4 weeks. Replacement of appropriate hormones may be required as the steroid dose is tapered.
  - For **Grade 3-4** events, treat with an initial dose of IV corticosteroids followed by oral corticosteroids. When symptoms improve to Grade 1 or less, steroid taper should be started and continued over no less than 4 weeks. Replacement of appropriate hormones may be required as the steroid dose is tapered.

- **Hyperthyroidism or Hypothyroidism:**

Thyroid disorders can occur at any time during treatment. Monitor patients for changes in thyroid function (at the start of treatment, periodically during treatment, and as indicated based on clinical evaluation) and for clinical signs and symptoms of thyroid disorders.

- **Grade 2** hyperthyroidism events (and **Grade 2-4** hypothyroidism):
  - In hyperthyroidism, non-selective beta-blockers (e.g. propranolol) are suggested as initial therapy.
  - In hypothyroidism, thyroid hormone replacement therapy, with levothyroxine or liothyroinine, is indicated per standard of care.
- **Grade 3-4** hyperthyroidism
  - Treat with an initial dose of IV corticosteroid followed by oral corticosteroids. When symptoms improve to Grade 1 or less, steroid taper should be started and continued over no less than 4 weeks. Replacement of appropriate hormones may be required as the steroid dose is tapered.

- **Hepatic:**

- For **Grade 2** events, monitor liver function tests more frequently until returned to baseline values (consider weekly).
  - Treat with IV or oral corticosteroids
- For **Grade 3-4** events, treat with intravenous corticosteroids for 24 to 48 hours.
- When symptoms improve to Grade 1 or less, a steroid taper should be started and continued over no less than 4 weeks.

- **Renal Failure or Nephritis:**

- For **Grade 2** events, treat with corticosteroids.
- For **Grade 3-4** events, treat with systemic corticosteroids.
- When symptoms improve to Grade 1 or less, steroid taper should be started and continued over no less than 4 weeks.

- **Management of Infusion Reactions:** Signs and symptoms usually develop during or shortly after drug infusion and generally resolve completely within 24 hours of completion of infusion.

Table 6 below shows treatment guidelines for subjects who experience an infusion reaction associated with administration of pembrolizumab (MK-3475).

Table 6. Infusion Reaction Treatment Guidelines

NCI CTCAE Grade	Treatment	Premedication at subsequent dosing
Grade 1 Mild reaction; infusion interruption not indicated; intervention not indicated	Increase monitoring of vital signs as medically indicated until the subject is deemed medically stable in the opinion of the investigator.	None
Grade 2 Requires infusion interruption but responds promptly to symptomatic treatment (e.g., antihistamines, NSAIDS, narcotics, IV fluids); prophylactic medications indicated for <=24 hrs	
Stop Infusion and monitor symptoms.                      Additional appropriate medical therapy may include but is not limited to:
 
 
IV fluids
 
Antihistamines
 
NSAIDS
 
Acetaminophen
 
Narcotics
 
 
Increase monitoring of vital signs as medically indicated until the subject is deemed medically stable in the opinion of the investigator.                      If symptoms resolve within one hour of stopping drug infusion, the infusion may be restarted at 50% of the original infusion rate (e.g., from 100 mL/hr to 50 mL/hr). Otherwise dosing will be held until symptoms resolve and the subject should be premedicated for the next scheduled dose.
 
Subjects who develop Grade 2 toxicity despite adequate premedication should be permanently discontinued from further trial treatment administration.
	Subject may be premedicated 1.5h ( $\pm$ 30 minutes) prior to infusion of pembrolizumab (MK-3475) with:  Diphenhydramine 50 mg po (or equivalent dose of antihistamine).  Acetaminophen 500-1000 mg po (or equivalent dose of antipyretic).
Grades 3 or 4	Stop Infusion. Additional appropriate medical therapy may include but is not limited to: 
 
IV fluids
 
Antihistamines
 
NSAIDS
 
Acetaminophen
 
Narcotics
 
Oxygen
 
Pressors
 
Corticosteroids
 
Epinephrine
 
	No subsequent dosing
Grade 3: Prolonged (i.e., not rapidly responsive to symptomatic medication and/or brief interruption of infusion); recurrence of symptoms following initial improvement; hospitalization indicated for other clinical sequelae (e.g., renal impairment, pulmonary infiltrates)  Grade 4: Life-threatening; pressor or ventilatory support indicated	Increase monitoring of vital signs as medically indicated until the subject is deemed medically stable in the opinion of the investigator. Hospitalization may be indicated. 
Subject is permanently discontinued from further trial treatment administration.
	
Appropriate resuscitation equipment should be available in the room and a physician readily available during the period of drug administration.		

## 5.8 Diet/Activity/Other Considerations

### 5.8.1 Diet

Subjects should maintain a normal diet appropriate for patients with AML unless modifications are required to manage an AE such as diarrhea, nausea or vomiting.

### **5.8.2 Contraception**

Pembrolizumab and azacitidine may have adverse effects on a fetus in utero. Furthermore, it is not known if pembrolizumab and azacitidine have transient adverse effects on the composition of sperm.

For this trial, male subjects will be considered to be of non-reproductive potential if they have azoospermia (whether due to having had a vasectomy or due to an underlying medical condition).

Female subjects will be considered of non-reproductive potential if they are either:

(1) postmenopausal (defined as at least 12 months with no menses without an alternative medical cause; in women <45 years of age a high follicle stimulating hormone (FSH) level in the postmenopausal range may be used to confirm a post-menopausal state in women not using hormonal contraception or hormonal replacement therapy. In the absence of 12 months of amenorrhea, a single FSH measurement is insufficient.);

OR

(2) have had a hysterectomy and/or bilateral oophorectomy, bilateral salpingectomy or bilateral tubal ligation/occlusion, at least 6 weeks prior to screening;

OR

(3) has a congenital or acquired condition that prevents childbearing.

Female and male subjects of reproductive potential must agree to avoid becoming pregnant or impregnating a partner, respectively, while receiving study drug and for 120 days after the last dose of study drug by complying with one of the following:

(1) practice abstinence† from heterosexual activity;

OR

(2) use (or have their partner use) acceptable contraception during heterosexual activity.

Acceptable methods of contraception are‡:

Single method (one of the following is acceptable):

- intrauterine device (IUD)
- vasectomy of a female subject's male partner
- contraceptive rod implanted into the skin

Combination method (requires use of two of the following):

- diaphragm with spermicide (cannot be used in conjunction with cervical cap/spermicide)
- cervical cap with spermicide (nulliparous women only)
- contraceptive sponge (nulliparous women only)
- male condom or female condom (cannot be used together)
- hormonal contraceptive: oral contraceptive pill (estrogen/progestin pill or progestin-only pill), contraceptive skin patch, vaginal contraceptive ring, or subcutaneous contraceptive injection

†Abstinence (relative to heterosexual activity) can be used as the sole method of contraception if it is consistently employed as the subject's preferred and usual lifestyle and if considered acceptable by local regulatory agencies and ERCs/IRBs. Periodic abstinence (e.g., calendar, ovulation, sympto-thermal, post-ovulation methods, etc.) and withdrawal are not acceptable methods of contraception.

‡If a contraceptive method listed above is restricted by local regulations/guidelines, then it does not qualify as an acceptable method of contraception for subjects participating at sites in this country/region.

Subjects should be informed that taking the study medications may involve unknown risks to the fetus (unborn baby) if pregnancy were to occur during the study. In order to participate in the study subjects of childbearing potential must adhere to the contraception requirement (described above) from the day of study medication initiation (or 14 days prior to the initiation of study medication for oral contraception) throughout the study period up to 120 days after the last dose of trial therapy. If there is any question that a subject of childbearing potential will not reliably comply with the requirements for contraception, that subject should not be entered into the study.

### **5.8.3 Use in Pregnancy**

If a subject inadvertently becomes pregnant while on treatment with pembrolizumab and azacitidine, the subject will immediately be removed from the study. The site will contact the subject at least monthly and document the subject's status until the pregnancy has been completed or terminated. The outcome of the pregnancy will be reported to the Sponsor and to Merck without delay and within 24 hours to the Sponsor and within 2 working days to Merck

if the outcome is a serious adverse experience (e.g., death, abortion, congenital anomaly, or other disabling or life-threatening complication to the mother or newborn).

The study investigator will make every effort to obtain permission to follow the outcome of the pregnancy and report the condition of the fetus or newborn to the Sponsor. If a male subject impregnates his female partner the study personnel at the site must be informed immediately and the pregnancy reported to the Sponsor and to Merck and followed as described above and in Section 7.2.2.

#### **5.8.4 Use in Nursing Women**

It is unknown whether pembrolizumab or azacitidine are excreted in human milk. Since many drugs are excreted in human milk, and because of the potential for serious adverse reactions in the nursing infant, subjects who are breast-feeding are not eligible for enrollment.

### **5.9 Subject Withdrawal/Discontinuation Criteria**

Subjects may withdraw consent at any time for any reason or be dropped from the trial at the discretion of the investigator should any untoward effect occur. In addition, a subject may be withdrawn by the investigator or the Sponsor if enrollment into the trial is inappropriate, the trial plan is violated, or for administrative and/or other safety reasons. Specific details regarding discontinuation or withdrawal are provided in Section 7.1.4 – Other Procedures.

A subject must be discontinued from the trial for any of the following reasons:

- The subject or legal representative (such as a parent or legal guardian) withdraws consent.
- Failure to achieve  $\text{WBC} \leq 30 \times 10^9/\text{L}$  off hydroxyurea after 2 cycles of therapy.

*Note:* If increase in WBC is not leukemia-related such as seen with the use of steroids, infections, or growth factors and does not require hydroxyurea patient can remain on the study.

- Confirmed disease progression or relapse

*Note:* Please see Section 7.1.2.6 for explanation.

- Unacceptable adverse experiences as described in Section 5.2.1.4 and 5.2.1.5
- Intercurrent illness that prevents further administration of treatment
- Investigator's decision to withdraw the subject
- The subject has a confirmed positive serum pregnancy test

- Noncompliance with trial treatment or procedure requirements
- The subject is lost to follow-up
- Completed 24 months of treatment (interrupted or uninterrupted) with azacitidine and pembrolizumab. *Note: 24 months of study medication is calculated from the date of first dose. Subjects who stop azacitidine and pembrolizumab after 24 months may be eligible for up to one year of additional study treatment if they progress after stopping study treatment provided they meet the requirements detailed in Section 7.1.5.5*
- Administrative reasons

The End of Treatment and Follow-up visit procedures are listed in Section 6 (Protocol Flow Chart) and Section 7.1.5 (Visit Requirements). After the end of treatment, each subject will be followed for 30 days for adverse event monitoring (serious adverse events will be collected for 90 days after the end of treatment as described in Section 7.2.3.3.2). Subjects who discontinue for reasons other than progressive disease will have post-treatment follow-up for disease status until disease progression, initiating a non-study cancer treatment, withdrawing consent or becoming lost to follow-up. After documented disease progression each subject will be followed by telephone for overall survival until death, withdrawal of consent, or the end of the study, whichever occurs first.

### **5.9.1 Discontinuation of Study Therapy after CR**

Discontinuation of treatment after achievement of CR/CRI is not recommended and the goal would be to administer up to 24 months of treatment; however, discontinuation of treatment may be considered at the discretion of the investigator for subjects who have attained a confirmed CR/CRI that have been treated for at least 6 cycles with azacitidine/pembrolizumab and had at least four treatments (cycles) with azacitidine/pembrolizumab beyond the date when the initial CR/CRI was declared. Subjects who then experience disease relapse may be eligible for up to one year of additional treatment with azacitidine/pembrolizumab via the Second Course Phase at the discretion of the investigator if no cancer treatment was administered since the last dose of azacitidine/pembrolizumab, the subject meets the safety parameters listed in the Inclusion/Exclusion criteria, and the trial is open. Subjects will resume therapy at the same dose and schedule at the time of initial discontinuation. Additional details are provided in Section 7.1.5.5.

### **5.10 Subject Replacement Strategy**

#### **Safety Run In Phase:**

- If laboratory abnormalities and clinical situation exist on day 8 during cycle 1 precluding pembrolizumab administration, pembrolizumab administration can be delayed for 2 weeks, up to day 22, provided laboratory abnormalities correct themselves to the levels defined in Section 5.1 and clinical situation resolves/improves.

Patients who are ineligible for pembrolizumab administration by day 22 of cycle 1 will be removed from the study and replaced by another subject.

- If subject discontinue study treatment for any reason other than drug-related toxicity prior to completing 2 study cycles, this subject will be replaced.
- If subject discontinue study treatment before receiving a single dose of pembrolizumab, this subject will be replaced.

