## 2.0 TRIAL DESIGN

### 2.1 Trial Design

This is a multicenter, nonrandomized, open-label phase 2 study (with a safety run-in phase) of azacitidine (AZA) 75 mg/m^2 given IV or SQ on days 1-7 every 28 days in combination with pembrolizumab 200 mg given IV every 3 weeks (starting on day 8 of cycle 1). The dose/schedule of AZA selected for this study is FDA approved for patients with MDS/AML. The rationale for pembrolizumab dose/schedule- Section 4.2.2.

We plan to examine two AML patient cohorts:

**Cohort 1:** relapsed/refractory AML.

**Cohort 2:** newly diagnosed AML in older patients ( $\geq 65$  years) not candidates for induction chemotherapy.

Each cohort will be enrolled separately with distinct null hypotheses and statistical plans.

Azacitidine and pembrolizumab have distinct mechanisms of action with no common overlapping toxicities; however, as azacitidine and pembrolizumab have not been tested previously in combination in AML patients, we plan to start enrollment with **Cohort 1 (a safety run-in phase)** and include only relapsed/refractory AML patients excluding those relapsing after allogeneic hematopoietic stem cell transplant (alloHSCT).

**Cohort 1 (a safety run-in phase, 3 + 3 design):** The first three patients will be enrolled and receive planned azacitidine and pembrolizumab in cycle 1 (Section 2.2). If 0 or 1 patient of the first three patients have a DLT (dose limiting toxicity) in cycle 1, we will enroll additional 3 patients to better assess for toxicities. If less than 2 among first 6 patients experiences DLT in the cycle 1-3, we will open enrollment in Cohort 1 for all relapsed/refractory patients including those with prior history of alloHSCT and will also start to enroll patients in Cohort 2. We plan to monitor for DLTs up to the end of cycle 3 as some of immunological side effects associated with pembrolizumab may occur with the delay.

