### 5.2.1.3 Dose Limiting Criteria

- Dose limiting toxicities during **safety run in phase** will be determined during Cycle 1, Cycle 2, and Cycle 3 of study treatment. Adverse events that occur after the first three cycles will also be evaluated by investigator and may be considered as dose limiting.
- Subjects with AML have frequently  $\geq$  grade 3 cytopenias; thus, will be un-evaluable for hematologic DLT with the exception listed below.
- For hematologic toxicity, the only adverse event that will be considered dose limiting is:
  - grade  $\geq$  4 neutropenia and thrombocytopenia with a hypocellular bone marrow and no evidence of residual leukemia lasting for 42 days

NOTE: only patients evaluable for hematologic toxicity as defined in Section 5.2.1.5.2.1, 5.2.1.5.2.3 and Section 5.2.1.5.3 may need to have a bone marrow assessment after cycle 1 if no count recovery to baseline. Otherwise, all patients will have bone marrow after cycle 2);

- For non-hematologic toxicities, the only adverse events that will be considered dose-limiting are:

- Any grade 4 toxicity considered at least possibly related to study drugs excluding asymptomatic electrolyte aberrations that can be corrected to  $\leq$  grade 2 and excluding specific toxicities that are frequent in AML population such as fever, infections, fatigue, bleeding, bone pain.
- Any grade 3 toxicity considered at least possibly related to study drugs that does not resolve to  $\leq$  grade 2 within 48 hours with the exception of Grade 3 anorexia, nausea, vomiting, diarrhea, or mucositis if it resolves to  $\leq$  grade 2 within 72 hours of maximal supportive care; asymptomatic electrolyte abnormalities that can be corrected to  $\leq$  grade 2 and excluding specific toxicities that are frequent in AML population such as fever, infections, fatigue, bleeding, bone pain. Grade 3 neurotoxicity and nephrotoxicity of any duration will be considered dose-limiting if at least possibly drug-related.

Table 3. Safety Run In Phase- Dose De-escalation Rules

Number of patients with DLT during run in phase (Planned 6 patients)	Decision rule
0 or 1 out of 3 in Cycle 1	Enter 3 more patients
$\geq$ 2 of 3 in Cycle 1 OR $\geq$ 2 of 6 in Cycle 1	Patients will be assessed for safety. Based on the complete assessment of AEs, the dose reduction as proposed in the Section 2.1 and 2.2.

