### **8.2 Statistical Analysis Plan**

#### **8.2.1 Safety Run-In**

Each cohort will be enrolled separately with distinct null hypotheses and statistical plans. Since azacitidine and pembrolizumab have not been tested previously in combination in AML patients, we plan first to start enrollment with Cohort 1 (a safety run-in phase). Recognizing that Cohort 1 may also include patients who relapsed after allogeneic hematopoietic stem cell transplant (alloHSCT) and thus may have differential sensitivity (tolerability, immune-related adverse events [IRAEs]) to this drug combination, we will start enrollment in Cohort 1 to include patients who did not have prior alloHSCT.

The primary objective of the safety run-in is to determine the safety and tolerability of AZA followed by pembrolizumab in relapsed and refractory AML using a 3+3 design. We plan to monitor for DLTs in cycles 1, 2 and 3 as some of immunological side effects associated with pembrolizumab may occur with the delay. The first three patients will be enrolled and receive planned azacitidine and pembrolizumab in cycle 1. If 0 or 1 patient of the first three patients has a DLT (dose limiting toxicity) in cycle 1, we will enroll an additional 3 patients to better assess for toxicities. If less than 2 among first 6 patients experiences DLT in the cycle 1-3, we will open enrollment in Cohort 1 for all relapsed/refractory patients including those with prior history of alloHSCT and will also start to enroll patients in Cohort 2. If  $\geq 2$  of the first 3 patients or  $\geq 2$  of 6 patients have DLTs during cycle 1, we will perform safety (detailed toxicity) review to assess for disease versus treatment-related toxicities. Given that pembrolizumab is given only once in cycle 1 (day 8), we will first dose de-escalate azacitidine as detailed in Section 2.2. However, if the safety data analysis suggests that the toxicities are more likely pembrolizumab related, an alternative approach we may take is to exclude pembrolizumab in cycle 1 and start pembrolizumab dosing in cycle 2 when AML is better controlled but maintain azacitidine dose/schedule as described in Section 2.2. If

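### The run-in replaces patients who leave before completing 2 cycles, but the DLT window is 3 cycles, so patients leaving in between stay in the six without full cycle 3 exposure

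*Combined protocol and SAP*

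**What the plan says.** **Window.** Section 5.2.1.3 states that DLTs in the run-in "will be determined during Cycle 1, Cycle 2, and Cycle 3 of study treatment". Section 8.2.1 agrees: "We plan to monitor for DLTs in cycles 1, 2 and 3". Section 2.1 says "We plan to monitor for DLTs up to the end of cycle 3" and gives the reason, which is that some immune effects of pembrolizumab may come late.

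**Decision.** Sections 2.1 and 8.2.1 and Table 3 in 5.2.1.3 open phase 2 if fewer than 2 of the first 6 patients have a DLT in cycles 1 to 3.

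**Replacement.** Section 5.10 has three rules for the run-in:
- for a patient who stops for a reason other than drug-related toxicity "prior to completing 2 study cycles, this subject will be replaced";
- "Patients who are ineligible for pembrolizumab administration by day 22 of cycle 1 will be removed from the study and replaced by another subject";
- a patient who stops "before receiving a single dose of pembrolizumab, this subject will be replaced".

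**Evaluability.** The only wording on this is in 5.2.1.3, with the definitions in 5.2.1.5.2, and it concerns hematologic DLTs. For non-hematologic DLTs no minimum exposure or follow-up is stated.

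**The concern.** The replacement rule stops one cycle short of the window that it serves. A patient who completes cycle 2 and then leaves for a reason other than toxicity is not replaced. The two pembrolizumab rules do not reach that patient, who has already been dosed. With the denominator fixed at six, the patient in effect counts among those without a DLT, although the cycle 3 treatment was never given or not given in full.

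The shortfall falls in the part of the window that was added to catch delayed immune toxicity. If cycle 3 dosing adds any DLT risk, the error runs one way, towards opening phase 2.

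The protocol also places exits at this boundary. The marrow is examined after cycle 2. Section 5.9 requires discontinuation if the white cell threshold is not met off hydroxyurea after 2 cycles. Section 5.6.2 ends treatment for a leukemia-related white cell rise before cycle 3.

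**Working it through.** The documents give no operating characteristics for the run-in, so there is no stated figure to reproduce.

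**Exposure at the gap.** Cycles last 28 days (section 1.0), and pembrolizumab starts on day 8 and is given every 3 weeks (6.1, footnote a).
- DLT window: 3 × 28 = 84 days. Replacement cut-off: 2 × 28 = 56 days. The gap is days 57 to 84, one third of the window.
- Pembrolizumab on schedule: days 8, 29, 50 and 71. A patient stopping right after cycle 2 has had 3 of 4 doses.
- Azacitidine on schedule: 7 days per cycle, so 14 of 21 days.

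**Probability of opening phase 2.** Let q be the three-cycle DLT risk, e the DLT risk of a patient who leaves after cycle 2, and k the number of such leavers among the six. Then

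P(at most 1 of 6) = (1−q)^(6−k) (1−e)^k + (6−k) q (1−q)^(5−k) (1−e)^k + k e (1−e)^(k−1) (1−q)^(6−k).

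The values of q, e and k are assumptions. I take q = 0.33.

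*Full exposure (k = 0):* 0.67^6 + 6 × 0.33 × 0.67^5 = 0.0905 + 0.2673 = 0.358.

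*Upper bound:* leavers carry no cycle 3 risk.
- Even hazard: e = 1 − 0.67^(2/3) = 0.234.
- Late-loaded: e = 0.15 by the end of cycle 2, rising to 0.33 by the end of cycle 3 in those who stay.
- Example, k = 2 with even hazard: 0.1181 + 0.2328 + 0.0723 = 0.423.

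*Half of the cycle 3 risk kept:* e becomes e + 0.5 × (0.33 − e), which is 0.282 (even) or 0.240 (late-loaded).

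| Leavers | Upper bound, even | Upper bound, late | Half risk, even | Half risk, late |
|---|---|---|---|---|
| 0 | 0.358 | 0.358 | 0.358 | 0.358 |
| 1 | 0.390 | 0.418 | 0.374 | 0.388 |
| 2 | 0.423 | 0.484 | 0.390 | 0.419 |
| 3 | 0.458 | 0.555 | 0.407 | 0.452 |

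*A lower true rate:* at q = 0.20 the full-exposure value is 0.655. If 20% to 50% of the DLT probability falls in cycle 3 and leavers carry none of it (e = 0.16 to 0.10), the value is 0.672 to 0.696 with one leaver, 0.688 to 0.737 with two and 0.704 to 0.778 with three.

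**The case against.** **Follow-up continues after the last dose.** Section 7.1.5.3.1 sets the safety visit about 30 days after it. With a last pembrolizumab dose on day 50, that is about day 80 of 84. SAEs are collected for 90 days. Section 4.2.2 describes a long half-life and target engagement beyond 21 days, and 5.2.1.4 notes that immune events can appear months after the last dose. This stands, and it is why the zero-risk figures are only an upper bound. It does not restore cycle 3 dosing. New anticancer therapy also brings the safety visit forward (7.1.1.5.3) and can shorten SAE collection (7.2.3.3.2).

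**Exits after cycle 2 may be few.** Section 7.1.2.6 allows treatment past marrow or laboratory progression before 6 cycles. Eligibility requires a projected survival of at least 12 weeks, the length of the window. This also stands. Two or three leavers out of six is an assumption, and the documents give no rate of early progression. The white cell exits in 5.6.2 and 5.9 remain.

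**Later safeguards exist.** Investigators may judge events after cycle 3 to be dose limiting (5.2.1.3), safety is assessed after each cycle, and removals for toxicity are monitored every 5 patients (8.2.2.1). These limit the consequences of a wrong run-in decision, but they do not correct its denominator.

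**Stronger readings that a reader might infer.** One is that the plan states that leavers are DLT-free. It does not; this follows from the fixed six and the missing evaluability definition, and a leaver who had a DLT still counts as one. Another is that late toxicity in leavers goes unseen. The follow-up rules contradict that, since what is missing is mainly exposure. A third is that phase 2 was opened wrongly. The documents do not report how many run-in patients left after cycle 2.

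**Conclusion.** The inconsistency is explicit and should be reconciled. As written, the rules can leave patients without full cycle 3 exposure in the denominator of the decision that opens phase 2, and any resulting bias favours opening.

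Its size is modest to moderate and is illustrative only. At an assumed 33% risk, the probability of opening rises from 0.36 to between 0.37 and 0.42 with one leaver, 0.39 and 0.48 with two, and 0.41 and 0.56 with three. The lower ends assume even hazard with half the cycle 3 risk kept. The upper ends assume late-loaded risk with none kept, and should not be read as estimates.

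**What to change.** Reconcile 5.10 with 2.1, 5.2.1.3 and 8.2.1:
- Define a DLT-evaluable run-in patient as one who had a DLT at any time in cycles 1 to 3 or who completed the 3-cycle window.
- Replace in the run-in tally only patients who are not evaluable, and keep them in the safety and efficacy analyses.
- Apply the rule of at most 1 of 6 to evaluable patients.
- State how a patient who stops for drug-related toxicity short of a DLT is handled, since 5.10 at present does not replace that patient.

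Changing only the number of cycles in 5.10 from 2 to 3 would not be enough. A patient with a DLT who later left for progression would then be replaced, and the DLT could drop out of the tally.

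In a run-in still under way, the cost would be protocol wording, possibly a few replacement patients, and a slightly later decision. Here section 5.1.1 says that Cohort 1 has enrolled its 40 patients and that Cohort 2 is closed to accrual, so an amendment cannot alter the run-in decision. What remains is to report how many of the 6 run-in patients completed cycle 3 and the DLT tally among evaluable patients. That costs only a short tabulation of data already collected.
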